### 8.1 Adverse Event Follow-up

After the occurrence of an AE, the investigator is required to follow the subject proactively and provide further information on the subject's participation. Any device- or procedure-related SAEs, or SAEs involving the index limb will be followed up until the event resolves, the condition stabilizes, the event is otherwise explained, or the subject is lost to follow-up. Non-serious AEs that are relevant to the indication being studied, and other SAEs will be followed until adequately resolved or explained. The investigator will ensure that all follow-up information is provided to the Sponsor including results from any laboratory tests, investigations or consultations with other health care professionals that serve to clarify the nature of the event and/or cause of the event.

**8.2 Adverse Event Reporting**

All adverse events will be reported to the Sponsor as indicated in Table 2 below:

**Table 2: Overview of AE Reporting Timelines, Investigator/Site to Sponsor**

Type of Report	Submission Schedule
Acute Thrombosis Post Procedure	Verbal or written report within 24 hours of finding
Adverse Device Effect (ADE)	Written report within 5 working days
Unanticipated Adverse Device Effect (UADE)	Written report within 10 working days
Serious Adverse Event/Serious Adverse Device Effect (SAE/SADE)	Written report within 5 working days
Subject Death	Written report within 5 working days

The Investigator will report adverse events to the reviewing IRB/EC (*as applicable*) according to the institutional reporting requirements.

**8.3 Other Incident Reporting**

Incidents that occur during a clinical investigation must also be reported to the Sponsor. Table 3 below indicates potential incidents requiring reporting. There are unforeseen circumstances that may occur. Any item of incident or note must be reported to the Sponsor regardless of whether or not the item is listed. Reports must identify subjects using the study’s unique identifier to protect subject’s confidentiality.

**Table 3: Overview of Other Incident Reporting Timelines, Investigator/Site to Sponsor**

Type of Notification	Time Constraints
Withdrawal of IRB/EC Approval	Verbal report within 24 hours followed by a written report within 5 working days
Informed Consent NOT Obtained	Verbal or written report within 5 working days

**8.4 General AE Definitions**

An AE is defined as any undesirable clinical occurrence in a subject whether or not it is considered to be device related. In addition, the definition of AE applies to any event with an onset post study procedure or to any underlying diseases, present at baseline that exacerbate in severity post study procedure. Therefore, an underlying disease that was present at the time of enrollment is not reported as an AE, but any increase in the severity of the underlying disease is to be reported as an AE.

The following definitions for rating severity of adverse events will be used:

**Mild:** Awareness of signs or symptoms, but easily tolerated; are of minor irritant type; causing no loss of time from normal activities; symptoms would not require medication or a medical evaluation; signs or symptoms are transient. Consider whether these events are clinically significant and relevant to report.

**Moderate:** Interferes with the subject’s usual activity and/or requires symptomatic treatment.

**Severe:** Symptom(s) causing severe discomfort and significant impact of the subject’s usual activity and requires treatment.

**Serious adverse event (SAE)** is defined as an event:

- Results in death
- Is life-threatening
- Requires in-patient hospitalization or prolonged hospitalization
- Necessitates an intervention to prevent a permanent impairment of a body function or permanent damage to a body structure (i.e. revascularization of LimFlow System)
- Results in persistent or significant disability/incapacity
- Results in congenital abnormality

**Adverse Device Effect (ADE) / Device-Related Adverse Event:** an adverse effect on health or safety caused by or associated with the study device. An adverse event is considered to be device-related when, in the judgment of the investigator, the clinical event has a reasonable time sequence associated with use of the investigational device and is unlikely to be attributed to concurrent disease or other procedures or medications. It is reasonable to believe that the device directly caused or contributed to the adverse event.

**Procedure-Related Adverse Event:** an adverse event is considered to be procedure-related when it occurs within 30 days of the study procedure, and in the judgment of the investigator it is reasonable to believe that the event is associated with the study procedure and is not specific to the investigational device used. Other products, surgical techniques, or medications required specifically for the procedure are likely to have contributed to the occurrence of the event.

**Concomitant Medication-Related Adverse Event:** an adverse event is considered to be concomitant medication related when, in the judgment of the investigator, it is reasonable to believe that the event is associated with concomitant medications used in conjunction with the investigational device and is not otherwise specific to the investigational device (e.g., bleeding associated with anticoagulation medication).

**Pre-Existing Condition-Related Adverse Event:** an adverse event is considered to be related to a pre-existing condition when, in the judgment of the investigator, it is reasonable to believe that the event is associated with the subject's pre-existing condition and is not specific to the investigational device or procedure. Pre-existing conditions that are aggravated or become more severe during or after the procedure should be evaluated on a case-by-case basis to determine if the event may be more appropriately classified as device-related or procedure-related.

**Unanticipated Adverse Device Effect (UADE):** Any serious adverse effect on health or safety or any life-threatening problem or death caused by, or associated with the study device, if that effect, problem or death was not previously identified in nature, severity, or degree of incidence in the Investigational Plan or any other unanticipated serious problem associated with a device that relates to the rights, safety, or welfare of subjects.

The Sponsor, or its designee, will assess all adverse events considered to be serious and device-related for potential reportability to the FDA and other regulatory authorities as an Unanticipated Adverse Device Effect (UADE).

When reporting AEs, the presenting condition should be reported as the AE; any procedures performed would be reported as "treatment", and any deaths would be reported as outcomes. Example:

- Adverse Event: arterial or venous occlusion
- Treatment: re-interventions or amputation
- Outcome: resolved

### 8.5 General Reporting Requirements (Serious & Non-Serious Adverse Events)

All potentially device- and/or procedure-related adverse events (AE) and all serious adverse events (SAE) will be reported and monitored from the time of treatment through the 6-month follow-up visit. Any SAEs related to the index limb will be reported and monitored throughout the 3-year follow-up visit. The report should include: severity, duration, action taken, treatment outcome and relationship of the adverse experience to the study device, procedure, concomitant medications, pre-existing condition, etc. (i.e., unrelated, related or relationship unknown).

In the case of device- and/or procedure-related adverse events that require adjudication by the CEC, medical record source documentation (e.g., procedure notes, operative notes, discharge summary, relevant progress notes, imaging, photos, or lab studies) must be provided to Sponsor or its designee.

It is the responsibility of the investigator to inform their IRB/EC of serious adverse events as required by their IRB/EC procedures and in conformance with FDA and local regulatory requirements.

### 8.6 Reporting to Sponsor

All serious device- and/or procedure-related adverse events and any device malfunctions or failures should be reported by the investigator (or designee) to the Sponsor, within 5 working days of learning of the adverse event or failure via phone or email contact. The Sponsor contact information for reports and questions is:

Sponsor Contact:

LimFlow, Inc.

[contact]

[contact]

## 9. Protocol Deviations

Investigators must obtain prior approval from the Sponsor's clinical study management and in some cases, where applicable, the reviewing IRB/EC, before initiating *major* deviations from the protocol, except where necessary to protect the life or physical well-being of a subject in an emergency. Such approval shall be documented in writing and maintained in the clinical study management and Investigator files. Prior approval is generally not expected in situations where unforeseen circumstances are beyond the Investigator's control, (e.g., subject was not available for scheduled follow-up office visit, blood sample lost by laboratory, etc.); however, the event is still considered a deviation and will be reported on the appropriate CRF.

Deviations must be reported to Sponsor regardless of whether medically justifiable, outside the control of the Investigator, pre-approved by Sponsor, or taken to protect the subject in an emergency. Subject-specific deviations and other deviations (e.g., unauthorized use of an investigational device outside the study, unauthorized use of an investigational device by a physician who has not signed an Investigator agreement or not been trained in the use of the device, etc.) will be reported in the eCRF. Investigators will adhere to procedures for reporting study deviations to their IRB/EC in accordance with their specific reporting policies and procedures. AE source document worksheets (SDW) will be provided for documentation of Investigator's assessments/signature/date, which will be used to monitor relatedness data.

Regulations require that Investigators maintain accurate, complete, and current records, including documents showing the dates of and reasons for each deviation from the protocol. For reporting purposes, Sponsor classifies study deviations as major and minor:

**Major deviation:** Any deviation from subject inclusion and exclusion criteria, subject informed consent procedures, or unauthorized device use.

**Minor deviation:** Deviation from a protocol requirement such as incomplete/inadequate subject testing procedures, follow-ups performed outside specified time windows, etc.

Minor Deviations that continue to occur at an investigational site may be classified as Major Deviations if corrective action is not taken to secure future compliance to the protocol. Periodic listings of site-specific protocol deviations will be provided to the respective clinical sites throughout the course of the study.

## 10. Risk/Benefit Assessment

### 10.1 Potential Benefits

The potential benefit to the subjects enrolled in this study is improved blood flow to the foot, but not necessarily eliminating the need for major amputation. The potential benefit of improved wound healing greatly outweighs the standard endovascular/surgical risks associated with this procedure in this “no-hope” patient population who will have a major amputation if the LimFlow procedure is not attempted. However, the actual benefits are not known and are the subject of this investigational study. There may be no direct benefits of study participation. However, subject participants will undergo an enhanced level of clinical scrutiny of health compared to routine clinical care, which may provide some indirect health benefits.

### 10.2 Risk Analysis

The benefit to the subjects enrolled in this study is the potential for improved blood flow to the foot, reducing or eliminating the need for major amputation. The proposed clinical investigation is designed to gather evidence to support preliminary risk assessment and the subjects to be enrolled may be subject to both anticipated and unanticipated adverse events.

### 10.3 Anticipated Adverse Events

The following adverse events may occur as a result of anesthesia, use of contrast or the use of the investigational device. Listed below are the events that are considered to be anticipated when performing any percutaneous endovascular intervention and may be attributable to the use of the LimFlow System:

- Allergic response
- Arterial / venous occlusion
- Arterial / venous thrombus formation
- Arterio-venous fistula (unplanned)
- Bleeding / oozing from the puncture site
- Bruising at wound site
- Compartment syndrome
- Congestive cardiac failure
- Contrast-induced nephropathy and renal failure
- Death
- Device failure / malfunction
- Edema
- Embolization (air, tissue, device)
- Hematoma
- Infection
- Inflammatory response
- Intimal tear / dissection
- Lower extremity ischemia
- Occlusion of the stent graft
- Perforation of the vessel wall
- Peripheral nerve injury
- Pseudoaneurysm
- Requirement for major amputation of index limb
- Retroperitoneal bleeding
- Systemic infection, sepsis
- Vascular injury requiring repair
- Vasospasm
- Vasovagal response
- Wound dehiscence
- Wound site pain

The LimFlow System was reviewed in accordance with a risk management process that complies with the international standard on the application of risk management to medical devices EN ISO 14971:2012. The risk management process entailed an analysis of potential risks and an evaluation of their acceptability in the light of the intended therapeutic use of the system. The purpose of the risk analysis was to identify and characterize undesirable events that could result in harm. For each identified hazard the risks were estimated by factoring in the probability of occurrence and severity of the harm. The design verification report was reviewed to verify that all risk control measures identified as necessary to reduce risk to acceptable levels had been implemented and that no risks would arise from the implementation of control measures. It was concluded that all risks associated with the identified hazards had been reduced to acceptable levels and that the overall risk of the use of the LimFlow System was determined to be acceptable. The LimFlow System received CE-mark in October 2016.

### 10.4 Potential Risks to Subject Confidentiality

In all clinical studies, confidentiality of protected health information may be breached due to study-related activities beyond those of routine clinical care. This risk will be minimized by not collecting personally identifying information on Case Report Forms (CRFs) or other study related documentation to be provided to the study Sponsor. Such documentation will be linked to the subject using a unique study identification code.

### 10.5 Minimization of Anticipated Risks

The following steps have or will be taken by LimFlow, Inc. to control or mitigate the risks during the course of this study:

- The use of standard medical grade materials that have been thoroughly characterized and tested to assure biocompatibility.
- Extensive pre-clinical evaluation including in vitro bench testing, animal and cadaver study.
- The well-established, standard nature of the endovascular procedures and techniques to be used.
- The ability to quickly and safely remove the LimFlow System from the procedure; the physician may elect to discontinue the use of the device at any time in favor of alternate devices.
- Monitoring of angiographic and hemodynamic parameters during placement of the device to evaluate for any compromise of the subject's condition.
- Conducting frequent follow-up visits in the first year post-operatively to allow for systematic monitoring and surveillance of the index limb, allowing for early detection of hemodynamically significant stenosis in the graft that may occur in the absence of obvious symptoms.
- Screening of potential subjects by an independent committee to ensure that all subjects meet defined eligibility criteria.
- Selecting only qualified, experienced Investigators who have participated in an extensive training program to assure thorough knowledge of the Investigational Plan and proper technique for use of the LimFlow System.
- Providing clinical support for device related guidance during the implant procedure.
- Providing safety oversight by an independent group of physicians (the CEC and DMC) for individual subjects as well as across the entire study population.
- Attending to arterial and venous access techniques to minimize the trauma to vascular structures.
- Ensuring that treatment and follow-up of subjects is consistent with standard and current medical practice.
- If the DMC determines a negatively high rate for a particular safety issue across the subject population, a termination assessment will be performed, and the DMC may recommend enrollment in the study be stopped.
- PHI protection measures such as use of a unique study identification code and a commitment from all participants to protect subject confidentiality at every step during the investigation.

### 11. Statistical Analysis Plan

A single treatment arm will be enrolled to confirm the safety and effectiveness of the LimFlow System. The study will consist of a minimum of 60 and up to 120 subjects. This study utilizes a Bayesian Goldilocks adaptive design for sample size determination.

---

### 11.1 Analysis Overview

This design utilizes a Bayesian Goldilocks adaptive design for sample size determination. The pivotal cohort will consist of a minimum of 60 subjects and a maximum of 120 subjects. When N=60 subjects have been enrolled in this cohort, enrollment may stop based on a Bayesian predictive probability calculation of whether the study is likely to pass its primary endpoint hypothesis test. If enrollment does not stop, 15 more subjects will be enrolled (N=75 total in the pivotal cohort), and the process will be repeated. The repetition may continue up to a maximum of N=120 subjects in the pivotal cohort. Once enrollment stops, six months of follow-up will ensue, at the end of which the only primary endpoint hypothesis test will occur.

### 11.2 Statistical Hypotheses for the Primary Endpoint

The null and alternative hypotheses for the primary endpoint are:

$$H_0: \phi \leq 0.54$$

$$H_a: \phi > 0.54$$

where  $\phi$  is the proportion of subjects that are amputation-free at 180 days (i.e., AFS at 180 days).

#### 11.2.1 Criterion for Success

The value specified for  $\Psi$  in this study is  $\Psi = 0.977$ . Achieving probability  $\Pr(\phi > 0.54 \mid \text{data}) > \Psi$  at the final analysis will imply acceptance of the alternative hypothesis and will constitute evidence of study success.

#### 11.2.2 Determining the Performance Goal

The following is a summary of a report prepared for LimFlow by the Yale Cardiovascular Research Group, *Meta-Analytic Report for the LimFlow System Version 3* dated 10 March 2020.

A literature search was undertaken to identify published data on the long term (6 months or longer) clinical outcomes. Specifically: amputation-free survival or the composite of all-cause mortality or major [above-the-knee] amputation, all-cause mortality, major amputation, and wound healing) of patients with unintervened lower extremity critical limb ischemia (CLI) treated per the standard of care. Also, a literature search was performed to identify clinical data regarding the relative hazard of high-risk CLI patients (Rutherford category 5 or 6) in comparison with low-risk CLI patients (Rutherford category 4) for the outcomes of amputation-free survival, all-cause mortality, and major amputation.

The literature search was performed according to a pre-specified protocol, and the search methods and results have been documented in a Literature Search Report (“Literature Search Report for the LimFlow System” Version 2.0 dated 25 February 2020). The literature search identified 42 publications meeting inclusion criteria that reported amputation-free survival (AFS), the composite of all-cause death or major (above-the-knee) amputation, all-cause mortality, major amputation, or wound healing in no-option CLI patients.

Double data entry was performed to abstract the data into a Microsoft Excel spreadsheet, including study design variables, sample size, treatment arms, enrollment timeframe (month and year range), medical management (type, duration, and dose), patient demographics, baseline disease characteristics, and the selected clinical outcome measures at 6 and 12 months.

---

Of the 42 publications, 33 publications reported the 6- or 12-month rate of amputation free survival (or the composite of all-cause mortality or major amputation, which was converted into amputation free survival) and contributed to the meta-analysis. Of these, 29 studies reported AFS at six months, and 25 reported AFS at 12 months.

The observed event rates were extracted from each of the relevant studies and combined via a meta-analytic approach to arrive at an estimated historical AFS event rate for patients with no-option CLI. The pooled AFS rate estimate was calculated by taking the meta-analytic average using inverse variance weighting and a random-effects approach to account for the variability in the estimates and the potential heterogeneity of the studies. Confidence intervals around the pooled estimate were also calculated.

Table 4 shows details for each article included in the meta-analysis. The column labeled *Included Rutherford Categories* shows that many studies in Rutherford 4 (R4) as well as Rutherford 5 and 6 (R5, R6). The columns labeled *Observed Proportion R 5/6* shows the proportion of R5 and R6 patients in the study. Several studies did not report the proportion of R5 and R6, the proportion of patients in each Rutherford category, the proportion of high-risk patients was imputed based on the average of all studies that reported this proportion.

For studies only reporting patient classification by Fontaine Stage, and enrolled only Fontaine IV patients, it was not possible to determine the proportion of patients with Rutherford category four versus Rutherford category 5/6 disease. Some Fontaine IV patients would be classified as Rutherford category four because they did not meet both clinical and objective criteria for Rutherford category 5. The proportion of patients in each Rutherford category; the proportion of high-risk patients was, was also imputed based on the average of all studies that reported this proportion.

The proportions, either imputed or observed, are shown in the column labeled *Imputed or Observed Proportion R 5/6*.

The last column shows the risk-adjusted AFS rates. The risk adjustment was necessary since most studies reporting amputation-free survival in no-option CLI patients include subjects with R4, 5, and 6, and the OPG is based on R5/R6. Therefore, it was necessary to adjust the observed historical event rates to match that of the target patient population.

The initial approach to determining the adjustment factor was to perform another literature search for papers reporting the hazard ratios (HR) for AFS, all-cause mortality, or major amputation by Rutherford category in patients with CLI (regardless of revascularization status). Thirteen publications were identified, but only 3 provided the unadjusted HR for Rutherford category 5/6 versus Rutherford category four patients. An adjustment factor for AFS rates was calculated from the HRs reported in Table 5 by the following methodology. First, the HR was log-transformed, and a weighted average of the log HR was calculated and then inverted back to the arithmetic scale. The resulting risk adjustment factor for AFS rates was 2.18.

The adjustment factor was then applied to the observed AFS rates in the applicable studies of no-option CLI patients according to the proportion of high-risk (Rutherford category 5/6) and low-risk (Rutherford category  $\leq 4$ ) patients in each study to arrive at an adjusted AFS rate by using the following three equations and solving for the High-Risk AFS rate:

**Equation 1:** *Adjustment Factor = Hazard Rate for death or major amputation for the high-risk patients  $\div$  Hazard Rate for death or major amputation low-risk patients = (1 - High-Risk AFS)  $\div$  (1 - Low-Risk AFS) = Low Risk AFS  $\div$  High Risk AFS*

**Equation 2** *Observed AFS Rate = High Risk % \* High Risk AFS + Low Risk % \* Low Risk AFS*

**Equation 3** *Low Risk AFS = High Risk AFS/adjustment*

The adjusted AFS rate for each paper is reported in the last column of Table 4.

The pooled AFS rate estimate was calculated by taking the meta-analytic average using inverse variance weighting and a random-effects model. This approach accounts for the variability in the estimates and the potential heterogeneity of the studies (see Meta-Analytic Average at the bottom of the last column in Table 4. Confidence intervals around the pooled estimate were also calculated. The meta-analytic estimate of the historical rate of AFS at six months in no-option patients with Rutherford category 5 or 6 CLI was 42.3% (95% CI, 33.5-51.1).

The performance goal is set at 54%, which is 2.9% higher than the upper 95% confidence limit of 51.1%.

**Table 4: Meta-analysis of 6-month AFS rate in no-option patients with Rutherford category 5 or 6 CLI (Original from Version 3.0 of Meta-Analytic Report)**

Study	N	Event-free survivors (n)	Observed AFS Rate	Included Rutherford Categories	Observed Proportion R4	Observed Proportion R 5/6	Imputed or Observed Proportion R 5/6	Adjusted AFS Rate
Brass et al 2006 	177	146	82.5%	4, 5, 6	NR	NR	66.0%	58.9%
Teraa et al. 2015 	79	66	83.5%	3, 4, 5, 6	31.6%	63.3%	63.3%	58.3%
Dubsky et al. 2013 	22	10	45.5%	4, 5, 6	NR	NR	66.0%	32.4%
Iafrafi et al. 2016 	34	22	64.7%	5	0.0%	100.0%	100.0%	64.7%
Anghel et al. 2011 	14	3	21.4%	4,5	50.0%	50.0%	50.0%	13.5%
Li et al. 2013 	29	22	75.9%	4, 5, 6	NR	NR	66.0%	54.1%
Benoit et al. 2011 	14	9	64.3%	4,5	50.0%	50.0%	50.0%	40.4%
Gupta et al. 2013 	10	8	80.0%	4, 5, 6	20.0%	80.0%	80.0%	64.7%
Szabo et al 2013 	10	4	40.0%	4, 5, 6	NR	NR	66.0%	28.5%
Belch et al. 2011 	259	196	75.7%	4, 5, 6	NR	NR	66.0%	54.0%
Losordo et al. 2012 	12	8	66.7%	4,5	41.7%	58.3%	58.3%	44.7%
Nikol et al. 2008 	56	34	60.7%	4, 5, 6	NR	NR	66.0%	43.3%
Powell et al. 2012 	24	17	70.8%	4, 5, 6	NR	NR	66.0%	50.5%
Idei et al. 2011 	30	3	10.0%	4, 5, 6	27.0%	73.0%	73.0%	7.6%
Pignon et al. 2017 	19	14	73.7%	4,5	35.0%	65.0%	65.0%	52.1%
Wang et al. 2018 	36	28	77.8%	4,5	66.7%	33.3%	33.3%	43.5%
Lindeman et al. 2018 	25	21	84.0%	3,4,5,6	8.0%	56.0%	56.0%	55.3%
Faglia et al. 2010 	27	3	11.1%	4,5,6	37.0%	63.0%	63.0%	7.7%
Dalla Paola et al. 2019 	84	50	59.5%	4,5,6	NR	NR	66.0%	42.5%
Dubsky et al. 2019 	44	31	70.5%	4,5,6	NR	NR	66.0%	50.3%
Faglia et al. 2012 	12	3	25.0%	5,6	0.0%	100.0%	100.0%	25.0%
Simple Average			59.2%	Simple Average			42.5%	
Weighted Average			68.6%	Weighted Average			49.0%	
Meta-Analytic Average			59.7%	Meta-Analytic Average			42.3%	
Min			10.0%	Min			7.6%	
Max			84.0%	Max			64.7%	
SD			24.0%	SD			17.4%	

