**Table 5: Publications reporting unadjusted HR for Rutherford Category 5/6 v. Rutherford Category 4**

Study	N	Patient Risk Profile	Variable	Event	Unadjusted Hazard Ratio	95% CI
Chung et al. 2013	98	Rutherford 4/5/6	R 5/6 vs. R4	AFS	1.56	1.01 - 2.41
Soga et al. 2014	995	Rutherford 4/5/6	R 5 vs. R 4	Death	2.3	1.6 - 3.3
Spreen et al. 2016	281	Rutherford 4/5/6	Rutherford 5/6 vs. Rutherford 4	Major Amputation	2.03	1.28 - 3.21

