Meta-analysis of 6-month AFS rate in no-option patients with Rutherford category 5 or 6 CLI**

Study	N	Event-free survivors (n)	Observed AFS Rate	Included Rutherford Categories	Observed Proportion R4	Observed Proportion R 5/6	Imputed Proportion R 5/6	Adjusted AFS Rate
Brass et al 2006 ³	177	146	82.5%	4, 5, 6	NR	NR	66.9%	59.3%
Teraa et al. 2015 ⁴	79	66	83.5%	3, 4, 5, 6	31.6%	63.3%	NA	58.3%
Dubsky et al. 2013 ⁵	22	10	45.5%	4, 5, 6	NR	NR	66.9%	32.7%
Iafrafi et al. 2016 ⁶	34	22	64.7%	5	0.0%	100.0%	NA	64.7%
Anghel et al. 2011 ¹¹	14	3	21.4%	4,5	50.0%	50.0%	NA	13.5%
Li et al. 2013 ¹²	29	23	79.3%	4, 5, 6	NR	NR	66.9%	57.0%
Benoit et al. 2011 ¹³	14	9	64.3%	4,5	50.0%	50.0%	NA	40.4%
Gupta et al. 2013 ¹⁴	10	8	80.0%	4, 5, 6	20.0%	80.0%	NA	64.7%
Szabo et al 2013 ¹⁷	10	4	40.0%	4, 5, 6	NR	NR	66.9%	28.8%
Belch et al. 2011 ¹⁸	259	196	75.7%	4, 5, 6	NR	NR	66.9%	54.4%
Losordo et al. 2012 ¹⁹	12	8	66.7%	4,5	41.7%	58.3%	NA	44.7%
Nikol et al. 2008 ²⁰	56	34	60.7%	4, 5, 6	NR	NR	66.9%	43.7%
Powell et al. 2012 ²¹	24	17	70.8%	4, 5, 6	NR	NR	66.9%	50.9%
Idei et al. 2011 ²²	30	3	10.0%	4, 5, 6	27.0%	73.0%	NA	7.6%
Pignon et al. 2017 ¹⁶	19	14	73.7%	4,5	35.0%	65.0%	NA	52.1%
Wang et al. 2018 ²⁴	36	28	77.8%	4,5	66.7%	33.3%	NA	43.5%
Faglia et al. 2010 ²⁵	27	3	11.1%	4,5,6	37.0%	63.0%	NA	7.7%
Dalla Paola et al. 2019 ²⁶	84	50	59.5%	4,5,6	NR	NR	66.9%	42.8%
Dubsky et al. 2019 ²⁷	44	31	70.5%	4,5,6	NR	NR	66.9%	50.7%
Faglia et al. 2012 ²⁸	12	3	25.0%	5,6	0.0%	100.0%	NA	25.0%
Simple Average			58.1%	Simple Average				42.1%
Weighted Average			68.3%	Weighted Average				49.2%
Meta-Analytic Average			58.6%	Meta-Analytic Average				42.0%
Min			10.0%	Min				7.6%
Max			83.5%	Max				64.7%
SD			24.1%	SD				17.7%

Meta-analytic estimate of the historical rate of AFS at 6 months in no-option R5/R6 CLTI patients is 42.0% (95% CI, 32.8-51.2).

STATISTICAL ANALYSIS PLAN

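### The 2.18 adjustment factor rests on unstated weights that match patient number and is treated as exact; with inverse-variance weights the 54% goal clears the historical upper limit by about 0.4 to 0.5 point, not 2.9

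*Protocol*

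**What the plan says.** Protocol section 11.2.2 derives the performance goal in three steps.

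- **Factor.** Table 5, "Publications reporting unadjusted HR for Rutherford Category 5/6 v. Rutherford Category 4", lists three studies. After log transformation, "a weighted average of the log HR was calculated and then inverted back to the arithmetic scale". The section then reports "The resulting risk adjustment factor for AFS rates was 2.18". It gives neither the weights nor an interval for the factor.
- **Adjustment.** Each study's observed AFS is treated as a mixture of high-risk and low-risk AFS, and the factor is used to solve for the high-risk rate (Equations 1 to 3, last column of Table 4).
- **Pooling and goal.** The adjusted rates are combined as a "meta-analytic average using inverse variance weighting and a random-effects model", giving 42.3% (33.5-51.1). The section concludes: "The performance goal is set at 54%, which is 2.9% higher than the upper 95% confidence limit of 51.1" per cent.

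SAP Appendix 1 gives a different rationale. Its Table 7 carries the note "Meta-analytic estimate of the historical rate of AFS at 6 months in no-option R5/R6 CLTI patients is 42.0% (95% CI, 32.8-51.2" per cent), but it keeps the goal that came from an earlier estimate of 43.7% with an upper limit of 53.5%, rounded up to 54%. The SAP describes an odds-ratio adjustment (2.891) and never prints 2.18.

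**The concern.** The trial is single-arm, so the historical rate is its only comparator. The protocol presents 54% as nearly three points clear of what history could plausibly have produced. That clearance depends on one number, 2.18, pooled from three ratios on three different events: AFS, death and major amputation.

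Patient number does not measure the precision of a hazard ratio. If it was the weight, the 995-patient study counts ten times as much as the 98-patient study, although by their printed intervals it carries only about 1.4 times the information. That study's ratio is also the one least matched to the use made of it: the event is death alone, and the comparison is Rutherford 5 with 4, without category 6. The only ratio for AFS itself, 1.56, would receive 7%.

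The interval of 33.5-51.1 could also be too narrow, if it omits the error in the factor.

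**Working it through.** **Inputs (protocol Table 5).** The SE of each log HR is (ln upper − ln lower)/3.92.

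| Event | N | HR (95% CI) | ln HR | SE | 1/SE² |
|---|---|---|---|---|---|
| AFS | 98 | 1.56 (1.01-2.41) | 0.445 | 0.222 | 20.3 |
| Death, R5 vs R4 | 995 | 2.3 (1.6-3.3) | 0.833 | 0.185 | 29.3 |
| Major amputation | 281 | 2.03 (1.28-3.21) | 0.708 | 0.235 | 18.2 |

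**Step 1: reproduce 2.18.** Factor = exp(Σw·ln HR / Σw).

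- Patient number (7.1%, 72.4%, 20.5%): exp(0.780) = 2.181, as stated
- Square root of N: 2.08
- Equal weights: 1.94
- Inverse variance (30.0%, 43.2%, 26.8%): exp(0.683) = 1.98

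For inverse variance the pooled log SE is 1/√(20.3 + 29.3 + 18.2) = 0.121, giving a 95% CI of 1.56-2.51. Heterogeneity is Q = 1.82 on 2 degrees of freedom, so the between-study variance is estimated as zero and fixed and random effects agree.

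**Step 2: reproduce Table 4.** With Low AFS = f × High AFS, as in the last equality of Equation 1, High AFS = Observed/[p + (1 − p)f]. For the 177-patient study at f = 2.18: 0.825/(0.66 + 0.34 × 2.18) = 0.825/1.401 = 58.9%, as printed. All 21 rows agree within 0.1 point. (Equation 3 as printed divides by the factor instead. Table 4 does not follow it.)

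**Step 3: reproduce the pooled rate.** DerSimonian-Laird random effects on the 21 printed rates, with variance rate × (1 − rate)/n, gives 42.3% (33.5-51.1), exactly as stated. Only sampling error and between-study variance enter, so the printed interval contains nothing for error in the factor.

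**Step 4: change only the factor to 1.98.** The result is 44.4% (35.3-53.55). The margin is 54 − 53.55 = 0.45 point instead of 2.9, a loss of about 85%. Two other pooling choices, REML and a rescaled variance, give upper limits of 50.1-50.3% at 2.18, so they do not reproduce the protocol, and 52.6-52.7% at 1.98. The shift is about 2.4-2.5 points in each case. The limit reaches 54% at a factor of about 1.94.

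**Step 5: carry the factor's uncertainty.** From steps 3 and 4 the pooled rate moves by (44.44 − 42.33)/(ln 2.18 − ln 1.98) = 2.11/0.0962 = 21.9 points per unit of log factor.

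- At 2.18: the log SE of the patient-number average is 0.143 and the pooled SE is (51.1 − 33.5)/3.92 = 4.5 points. Combined SE = √(4.50² + (21.9 × 0.143)²) = 5.48. Upper limit = 42.3 + 1.96 × 5.48 = 53.1%.
- At 1.98: √(4.65² + (21.9 × 0.121)²) = 5.35. Upper limit = 44.4 + 1.96 × 5.35 = 54.9%.

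Simulation, which allows for skewness, gives 53.3-53.4% and 55.2-55.4%. Rounded ranges: 53-53.5% and 55-55.5%.

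**Step 6: SAP Table 7.** The same method on its 20 rows at 2.18 reproduces 42.0% (32.8-51.2), so the same factor lies behind that table. At 1.98 it gives 44.0% (34.6-53.5).

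**For reference.** The AFS-only ratio of 1.56, from one study of 98 patients, would give 49.8% (40.0-59.5).

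**The case against.** Several points on the other side stand.

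- **No arithmetic error is shown.** The figure 2.18 is a correct weighted average under some set of weights. That the weights are patient numbers is an inference, because the meta-analytic report that would state them is not part of the plan. The interval for 1.98 contains 2.18, and 1.98 still averages three different endpoints.
- **54% still clears the re-weighted limit.** A reader might infer that re-weighting alone puts the goal inside the historical interval. It does not: 53.55% is below 54%. The limit passes 54% only when the precision-weighted factor is used and its uncertainty is also carried.
- **The SAP claims no more.** A limit of 53.5% rounded up to 54% is a clearance of 0.5 point, about what step 4 finds. No test, threshold or simulation uses the 2.9.
- **A result just above 54% could not succeed.** A reader might infer that a weak result would be declared a win. With complete data and the Beta(1,1) prior, exceeding 0.977 needs 41/60 (68.3%), 50/75 (66.7%), 59/90 (65.6%) or 67/105 (63.8%).
- **The size depends on the scale.** The plan uses a hazard ratio as a ratio of survival proportions. Applied as a hazard ratio (Low = High^(1/f)), the same pool has upper limits of 66.7% at 2.18 and 66.9% at 1.98, a shift of about 0.25 point. The scale is a separate and larger question, but the 2.4-point effect cannot be quoted without it.

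What remains is that the protocol states a margin and an interval that its own inputs and its own pooling method do not support.

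**Conclusion.** The point holds as a matter of how the comparator is justified. The stated 2.9-point margin depends on an undisclosed weighting that differs from the method used elsewhere in the section, and on treating an average of three ratios as known. With inverse-variance weights the margin is about 0.4-0.5 point, and once the factor's uncertainty is included there is none. Even with 2.18 kept, carrying its uncertainty cuts the margin to between about 0.5 and 1 point.

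This rests on three assumptions: the weights are patient numbers (inferred from the match), the printed confidence intervals are symmetric on the log scale, and the plan's survival-ratio adjustment is retained.

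The consequence concerns the true rate, or the lower credible bound. A success establishes that AFS exceeds 54%. If the historical upper limit is nearer 55%, a lower bound only just above 54% does not by itself exclude it. The documents do not support going further and saying that the hypothesis test is invalid or that the goal must be moved.

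**What to change.** **Protocol section 11.2.2**

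- State the weights behind the factor.
- Use the inverse-variance value with its interval, 1.98 (1.56-2.51), and carry that uncertainty into the 95% CI of the historical rate.
- Restate the historical rate and limit, and replace the 2.9% sentence with the recomputed margin: about 0.4-0.5 point before factor uncertainty, none after.

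**SAP Appendix 1**

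- Note that Table 7's adjusted rates reproduce with 2.18, and give the result at 1.98: 44.0% (34.6-53.5).
- Reconcile the SAP's rationale for 54% (53.5% rounded up) with the protocol's (2.9 points above 51.1%).

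**Analysis**

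- Keep the 0.54 hypothesis and the 0.977 threshold.
- As a supportive summary, report the posterior probability that AFS exceeds the recomputed upper limit. No other cut-off is needed.

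Make these changes together with any correction of the scale on which the hazard ratio is applied. Otherwise the new figures would themselves need replacing.

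The cost is some text and a re-run of an existing calculation. Sample size, stopping rules and type I error are untouched. The downside is a less favourable stated margin.
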